11.1 Determination of Sample Size

For subjects with psoriasis vulgaris, the number of relapses per year is assumed to be between 4 and 8. We assume that the time to event (first relapse) is a Poisson process, i.e. that events occur continuously and independently at a constant rate. Then the time between events is given by the exponential distribution. Time to event is analysed by means of the hazard function, which can be thought of as the probability of experiencing an event now if you have not experienced one already. [Table 16](#) shows the mean and median waiting times as well as hazards according to number of relapses per year.

Table 16: Mean and median waiting times and hazards according to number of relapses per year

	Number of relapses per year		
	4	6	8
Mean waiting time (weeks)	13.00	8.67	6.50
Median waiting time (weeks)	9.01	6.01	4.51
Hazard	0.077	0.115	0.154

The drop-out rate observed in a long-term trial with calcipotriol/BDP ointment (MCB 0102 INT) was about 30 % over 52 weeks. Assuming an exponential decline this corresponds to a median waiting time for drop out at about 101 weeks. We assume that the same will be the case in this trial and that between 4 to 8 relapses will occur per year in the vehicle group.

A 30 percent reduction in hazard, i.e. a hazard ratio of 0.7 for active treatment group relative to vehicle group is considered to be of clinical interest.

With the above assumptions it follows using a two sample survival test that for detecting a hazard ratio of 0.7 for active treatment group relative to vehicle group, between 178 and 190 subjects per group are needed in order to obtain a power of 90% for a 5% significance level. Thus, 380 subjects should be randomised.

In previous trials in similar populations, approximately 48% subjects treated with LEO 90100 aerosol foam achieved treatment success after 4 weeks of treatment. Assuming a binomial distribution with 48 % probability of success it is estimated that 832 subjects should be included in the trial in order to have 90 % probability of achieving at least 380 subjects to be randomised.

For the HPA axis testing, the aim is to achieve approximately 25 subjects undergoing HPA axis testing after 52 weeks of exposure.

The total number of subjects treated in the trial should also be sufficient to comply with ICH E1 regarding long-term safety. The aim is to achieve at least 300 subjects with 26 weeks of exposure and at least 100 subjects with 52 weeks of exposure.

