11.3.5.1 Dermatology Life Quality Index (DLQI)

A DLQI total score is the sum of the 10 equal-weighted questions and ranges from 0 (no quality of life impairment) to 30 (maximal quality of life impairment).

During the open-label treatment phase, the total DLQI score will be summarised over time.

During the maintenance phase, the total DLQI score will be summarised over time by treatment group. The total DLQI score will also be summarised over time by treatment group and relapse status, i.e. according to whether or not the subject has a confirmed relapse at that visit.

At 12 and 52 weeks after randomization the mean DLQI will be compared between treatment groups for the full analysis set using a t-test. The comparison will be done both using observed data only and using last observation carried forward. Treatment differences, p-values and confidence intervals will be presented.

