11.3.5.4 Psoriasis Symptom Inventory

The total psoriasis symptom inventory score as well as each of the 8 individual scores will be summarised over time both for the open-label treatment phase, and for the maintenance phase by treatment group.

At 12 and 52 weeks after randomisation the mean total psoriasis symptom inventory score will be compared between treatment groups for the full analysis set using a t-test. The comparison will be done both using observed data only and using last observation carried forward. Treatment differences, p-values and confidence intervals will be presented.

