For each of the 100 complete datasets the total DLQI scores will be analysed using a Mixed effect Model Repeated Measurement (MMRM) with treatment group, visit (scheduled), interaction between treatment and visit, relapse status, and maintenance baseline total DLQI score as fixed factors and subject as random effect. Repeated measurements within subject is modelled using an unstructured variance structure. REML will be used for estimation.

The estimates and standard errors from the 100 analyses will be pooled into estimated least squares means for each treatment group and estimated treatment difference with associated standard errors using Rubin's rule to draw inference. From these pooled treatment estimates, the 95% CI for the treatment difference will be calculated. The p-value for treatment difference will be calculated using a two-tailed Student's t-test based on the pooled estimate. Pooled treatment estimates together with treatment difference, 95% CI and p-value will be presented by visit. Furthermore, the pooled treatment estimates will be plotted by visit.

See section [5.7](#) for details regarding changes as compared to the protocol.

More details for the tables and listings can be found in [Appendix I](#) and [Appendix II](#).

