-----------------------	-------------------	--------------------------------

Statistical analysis:

For each of the 100 complete data sets, the total PSI scores will be analysed using a Mixed effect Model Repeat Measurement (MMRM) with treatment group, week (from randomisation), interaction between treatment and week, relapse status, and maintenance baseline total PSI score as fixed factors and subject as random effect. Repeated measurements within subject is modelled using an unstructured variance structure. REML will be used for estimation.

The estimates and standard errors from the 100 analyses will be pooled into estimated least squares means for each treatment group and estimated treatment difference with associated standard errors using Rubin's rule to draw inference. From these pooled treatment estimates, the 95% CI for the treatment difference will be calculated. The p-value for treatment difference will be calculated using a two-tailed Student's t-test based on the pooled estimate. Pooled treatment estimates together with treatment difference, 95% CI and p-value will be presented by week. Furthermore, the pooled treatment estimates will be plotted by week.

Subjects are supposed to complete the PSI questionnaire on a weekly basis the first 28 weeks of the maintenance phase and the 2 last weeks of the maintenance phase (Week 54 to 56) which is only applicable for completers. However, during blind review of data, it is observed that subjects in general forget to complete the questionnaire the last 2 weeks which implies that limited data are available for this period. For this reason, the analysis of the PSI total score will be based on the first 28 weeks of the maintenance phase.

The analysis of PSI will be done for full analysis set.

More details for the tables and listings can be found in [Appendix I](#) and [Appendix II](#).

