Section 5.4.3.6	Time to first relapse according to m-PASI	m-PASI and PGA are both tools for assessing the psoriasis severity and will therefore be mutually related. Since rescue IMP will be given to patients in relapse (based on the PGA) y, the level of m-PASI might also be affected. Therefore, the observed progress in m-PASI over time might be confounded with the rescue IMP. For this reason, time to first relapse according to m-PASI, will not be analysed (protocol section 11.3.4.4).
Section 5.4.3.8	Target lesion/location scores	In the protocol section 11.3.4.6 it is described that the endpoint will be summarised by visit. Since per protocol subjects will be withdrawn when not achieving 'clear' or 'almost clear' according to PGA after rescue IMP, the subset of subject's available values at the visits will be a selected population (most likely are subjects who responds well to the IMP). Hence summaries by visit will not be done. The summaries will be done only for data capture at the start or the end of a relapse period. See section 5.4.3.8 .

Section 5.4.3.9	Body surface area	
In the protocol section 11.3.4.7 it is described that the endpoint will be summarised by visit. Since per protocol subjects will be withdrawn when not achieving 'clear' or 'almost clear' according to PGA after rescue IMP, the subset of subject's available values at the visits will be a selected population (most likely are subjects who responds well to the IMP). Hence summaries by visit will not be done.
 
The summaries will be done only for data capture at the start or the end of a relapse period. See section 5.4.3.9.

Section 5.4.4.1	Total DLQI score	
In the protocol section 11.3.5.1 it is described that the endpoint will be summarised by visit. Since per protocol subjects will be withdrawn when not achieving 'clear' or 'almost clear' according to PGA after rescue IMP, the subset of subject's available values at the visits will be a selected population (most likely are subjects who responds well to the IMP). Hence summaries by visit will not be done.
 
The summaries will be done only for data capture at the start or the end of a relapse period. See section 5.4.4.1.
 
The analysis described in the protocol section 11.3.5.1 disregard the possible differences in withdrawal patterns between the two treatment groups. Instead multiple imputation for missing data and an MMRM analysis will be done. See section 5.4.4.1 for details.

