Section 5.4.4.2	EQ-5D-5L PSO	
In the protocol section 11.3.5.2 it is described that the endpoint will be summarised by visit. Since per protocol subjects will be withdrawn when not achieving 'clear' or 'almost clear' according to PGA after rescue IMP, the subset of subject's available values at the visits will be a selected population (most likely are subjects who responds well to the IMP). Hence summaries by visit will not be done.
 
The summaries will be done only for data capture at the start or the end of a relapse period. See section 5.4.4.2.

Section 5.4.4.4	PSI	
In the protocol section 11.3.5.1 it is described that the endpoint will be summarised over time. Since per protocol subjects will be withdrawn when not achieving 'clear' or 'almost clear' according to PGA after rescue IMP, the subset of subject's available values over time in the trial will be a selected population (most likely are subjects who responds well to the IMP). Hence summaries over time will not be done.
 
The summaries will be done using AUC over trial phases. See section 5.4.4.4 for details.
 
The analysis described in the protocol section 11.3.5.4 disregard the possible differences in withdrawal patterns between the two treatment

		groups. Instead multiple imputation for missing data and an MMRM analysis will be done. See section 5.4.4.1 for details.
Section 5.4.4.5	SGA	
In the protocol section 11.3.5.5 it is described that the endpoint will be summarised by visit. Since per protocol subjects will be withdrawn when not achieving 'clear' or 'almost clear' according to PGA after rescue IMP, the subset of subject's available values at the visits will be a selected population (most likely are subjects who responds well to the IMP). Hence summaries by visit will not be done.
 
The summaries will be done only for data capture at the start or the end of a relapse period. See section 5.4.4.5.

Trial ID: LP0053-1004	Date: 15-JUL-2019	Version: 1.0
		Page 47 of 177

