Treatment difference	
95% CI	
p-value	

Estimates are obtained from a Mixed effect Model Repeat Measurement (MMRM) including treatment group, days from randomisation, interaction between treatment and time, relapse status, PSI total score at time of randomisation. Multiple imputation is used to impute missing assessment of PSI. Rubin's rule is used to pool the estimates for the inference.

Shell 48: Statistical analysis of DLQI: full analysis set

LEO 90100 vs. vehicle	
Number of subjects randomised to LEO 90100	xxx
Number of subjects randomised to vehicle	xxx
Visit 2	
Estimated means	
LEO 90100	xx.xx
Vehicle	xx.xx
Treatment difference	xx.xx
95% CI	xx.xx-xx.xx
p-value	0.xxx or <0.001
...	
Visit 15	
Estimated means	
LEO 90100	
Vehicle	
Treatment difference	
95% CI	
p-value	

Estimates are obtained from a Mixed effect Model Repeat measurement (MMRM) including treatment group, days from randomisation, interaction between treatment and time, relapse status, DLQI total score at time of randomisation. Multiple imputation is used to impute missing assessment of DLQI. Rubin's rule is used to pool the estimates for the inference.

Shell 49: Shift table for EQ-5D-5L from start to end of open-label phase: open-label safety analysis set

Visit EQ-5D-5L	Open-label safety analysis set (n=xxx)					Randomised subjects (n=xxx)					Not randomised subjects (n=xxx)				
	Visit 2					Visit 2					Visit 2				
	0	1	2	3	4	0	1	2	3	4	0	1	2	3	4
Visit 1															
Mobility															
0: I have no problems walking	xxx	xxx	xxx	xxx	xxx	xxx	xxx	xxx	xxx	xxx	xxx	xxx	xxx	xxx	xxx
1: I have slight problems walking	xxx	xxx	xxx	xxx	xxx	xxx	xxx	xxx	xxx	xxx	xxx	xxx	xxx	xxx	xxx
2: I have moderate problems walking	xxx	xxx	xxx	xxx	xxx	xxx	xxx	xxx	xxx	xxx	xxx	xxx	xxx	xxx	xxx
3: I have severe problems walking	xxx	xxx	xxx	xxx	xxx	xxx	xxx	xxx	xxx	xxx	xxx	xxx	xxx	xxx	xxx
4: I am unable to walk	xxx	xxx	xxx	xxx	xxx	xxx	xxx	xxx	xxx	xxx	xxx	xxx	xxx	xxx	xxx
Self-care															
0: I have no problems washing or dressing myself	xxx	xxx	xxx	xxx	xxx	xxx	xxx	xxx	xxx	xxx	xxx	xxx	xxx	xxx	xxx
1: I have slight washing or dressing myself	xxx	xxx	xxx	xxx	xxx	xxx	xxx	xxx	xxx	xxx	xxx	xxx	xxx	xxx	xxx
2: I have moderate washing or dressing myself	xxx	xxx	xxx	xxx	xxx	xxx	xxx	xxx	xxx	xxx	xxx	xxx	xxx	xxx	xxx
3: I have severe washing or dressing myself	xxx	xxx	xxx	xxx	xxx	xxx	xxx	xxx	xxx	xxx	xxx	xxx	xxx	xxx	xxx
4: I am unable to wash or dress myself	xxx	xxx	xxx	xxx	xxx	xxx	xxx	xxx	xxx	xxx	xxx	xxx	xxx	xxx	xxx

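### The only tested DLQI and PSI models adjust for current relapse status, so their treatment difference leaves out the benefit of relapsing less often

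*SAP*

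**What the plan says.** SAP 5.4.4.1 analyses DLQI after multiple imputation with a mixed model for repeated measures. Its terms are treatment, scheduled visit, their interaction, and "relapse status, and maintenance baseline total DLQI score as fixed factors and subject as random effect". SAP 5.4.4.4 uses the same structure by week for PSI, with "relapse status, and maintenance baseline total PSI score as fixed factors and subject as random effect". The Shell 48 footnote in Appendix II repeats the term ("interaction between treatment and time, relapse status, DLQI total score at time of randomisation"), and the Shell 47 footnote does so for PSI. Each model yields a treatment difference, 95% CI and p-value at every visit or week.

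SAP 5.1 (Table 1) defines relapse as a PGA of at least mild during the maintenance phase. Protocol 11.3.3.3 uses the same PGA threshold for the primary endpoint, time to first relapse.

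The protocol planned something different. In 11.3.5.1, "the mean DLQI will be compared between treatment groups for the full analysis set using a t-test". In 11.3.5.4, "the mean total psoriasis symptom inventory score will be compared between treatment groups for the full analysis set using a t-test". Neither comparison adjusts for relapse; 11.3.5.1 uses relapse status only to split a descriptive summary. SAP 5.7 gives this reason for replacing the DLQI test: "The analysis described in the protocol section 11.3.5.1 disregard the possible differences in withdrawal patterns between the two treatment groups". It gives the same reason for PSI: "The analysis described in the protocol section 11.3.5.4 disregard the possible differences in withdrawal patterns". It does not mention the relapse term. Appendix I lists one statistical analysis per outcome (Tables 2-64 and 2-91) and no version without the term.

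**The concern.** Relapse status is measured after randomisation, and the maintenance treatment is meant to change it. Protocol 3.3.2 hypothesises a longer time to relapse and fewer relapses. Part of any effect on quality of life or symptoms should therefore run through spending less time in relapse. A model that holds current relapse status fixed removes that part. What remains is any difference between arms within the same state, plus any carry-over from earlier relapses.

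Protocol 3.3.2 also describes the trial as a comparison of a proactive with a reactive strategy, with rescue available in both arms. Relapse and its treatment belong to the strategies compared and are not a nuisance to be adjusted out.

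DLQI and PSI are the only patient-reported outcomes given treatment p-values. Figures 2-13 and 2-14 will present the results simply as estimated treatment differences. A reader would take them as the overall effect of assignment, which is what the protocol's t-tests addressed. If patients benefit mainly through fewer relapses, the reported result could be close to no difference.

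**Working it through.** **Structure.** Neither model has a treatment-by-relapse term. At any visit the contrast between least-squares means is therefore the difference at one common relapse status, whatever weights are used for the means. This needs no numerical input.

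**Inputs for the size.**
- Relapse rate on vehicle, Protocol 11.1: "between 4 to 8 relapses will occur per year in the vehicle group".
- Hazard ratio 0.7 (Protocol 11.1), here also applied to repeat relapses.
- Length of a relapse period: 4 weeks of rescue (Protocol 6.1.1).
- Score difference between relapse and remission: not given in the documents. I assume 2 to 6 DLQI points.

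**Reproducing the plan's own figure.** The documents give no power or effect size for DLQI or PSI, so I checked the primary-endpoint sample size from the same inputs. Schoenfeld events = 4 × (1.960 + 1.282)² / (ln 0.7)² = 331. With 30% exponential drop-out over 52 weeks, the event probabilities (vehicle, active) are 0.906 and 0.849 at 4 relapses a year, giving 331 / 0.8775 / 2 = 189 per group. At 8 a year they are 0.957 and 0.938, giving 175. Freedman's formula (338 events) gives 193 and 179. The protocol states 178 to 190, so the inputs are read correctly.

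**Time in relapse.** With a mean time to relapse of m = 52/r weeks on vehicle and m/0.7 on active, the long-run share of time in relapse is 4/(m + 4) and 4/(m/0.7 + 4).

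| Relapses/year (r) | m (weeks) | Vehicle | Active | Gap (points) |
|---|---|---|---|---|
| 4 | 13.00 | 4/17.00 = 23.5% | 4/22.57 = 17.7% | 5.8 |
| 6 | 8.67 | 4/12.67 = 31.6% | 4/16.38 = 24.4% | 7.2 |
| 8 | 6.50 | 4/10.50 = 38.1% | 4/13.29 = 30.1% | 8.0 |

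Simulating 52 weeks from a start in remission gives 22.9% against 17.2% at 4 a year and 37.2% against 29.3% at 8 a year, a gap of 5.7 to 7.9 points.

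**Score removed.** Gap × score difference: 0.058 × 2 = 0.12 at the low end and 0.080 × 6 = 0.48 at the high end.

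**Model check.** Simulated trials had 272 patients per arm (SAP Table 8 totals 545 randomised), 13 visits, a baseline covariate, no direct treatment effect and relapse 2, 4 or 6 points worse. Between-subject SD was 3, within-subject SD 2 and relapse frailty SD 0 or 0.5, all assumed. There were 200 trials per scenario, fitted by generalised least squares with a random-intercept covariance.
- Without relapse status, the difference was −0.12 (4 a year, 2 points) and −0.49 (8 a year, 6 points).
- With relapse status, it was −0.005 and 0.007 in those two cases, and within ±0.03 in all 12 scenarios (Monte Carlo SE about 0.01).

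A separate least-squares check with 190 per arm agreed: −0.10 to −0.49 without the term, −0.01 to 0.03 with it.

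**The case against.** The strongest reply is that the omitted benefit is tested elsewhere. The primary and both secondary endpoints address relapse directly under multiplicity control, the stated hypothesis does not name DLQI or PSI, and a difference beyond PGA-defined relapse is a legitimate question. That is true, but it supports a labelled supplementary analysis. It does not make the conditional contrast the overall difference the protocol set out to test.

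For PSI, Shell 46 includes an AUC row over the whole maintenance-phase window by arm, so an unconditional comparison can be formed by hand. It carries no test. DLQI has no equivalent, since SAP 5.4.4.1 lists in-relapse values only. The shell footnotes do disclose the term; what is missing is a rationale and a statement of what the estimate means.

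The objections to the size have more force. The models do not say how relapse status is coded. Suppose it means a relapse confirmed at that visit, the wording of Protocol 11.3.5.1, and every relapse is found at a scheduled visit. The share at visit v is then R(v) = p × (1 − R(v−1)), with R(0) = 0 and p = 1 − exp(−4 × hazard). The mean gap over 13 visits is 4.8, 5.6 and 5.8 points at 4, 6 and 8 relapses a year, and single-visit gaps run from about 2 to 11. Patients on daily rescue may also score close to remission for part of a relapse period. No score difference is available for PSI, and the simulations did not use the planned unstructured covariance or imputation. All of this changes the amount removed, not the fact that it is removed.

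**Conclusion.** The concern holds. As written, the DLQI and PSI estimates, intervals and p-values describe the difference between arms at equal current relapse status, and no tested analysis gives the overall difference. The withdrawal patterns cited in SAP 5.7 can justify imputation and a repeated-measures model, but not this covariate.

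The structural conclusion is certain from the text. The size is modest and conditional: about 0.1 to 0.5 DLQI points on a 0 to 30 scale, assuming the protocol's relapse rates and hazard ratio, 4-week relapse periods and a 2 to 6 point worsening in relapse. It is somewhat smaller under visit-confirmed coding. The likely direction is to understate the treatment benefit. Both outcomes are outside the procedure in SAP 5.6.4, so the primary and secondary conclusions do not change. This should be corrected, but it does not threaten the trial's main result.

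**What to change.** Make the main DLQI and PSI analysis the repeated-measures model with treatment, visit or week, their interaction and the maintenance-baseline score, without relapse status. Keep the planned model as a supplementary analysis labelled as the difference at equal current relapse status, and state how relapse status is coded at visits that start, fall within or end a relapse. Record both points in the DLQI and PSI rows of SAP 5.7 and in the footnotes to Shells 47 and 48.

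The cost is one term removed from two models, with edits to two SAP paragraphs, two rows of 5.7 and two shell footnotes. The existing models are kept as supplementary, and no new data are needed.

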6.1.4 Maintenance phase

During the maintenance phase, subjects will apply the randomised maintenance IP twice weekly on trunk and limbs to the areas where lesions have cleared or almost cleared after treatment was initiated at baseline. Any additional non-active psoriatic lesions (i.e. lesions not present at baseline that have been cleared or almost cleared by rescue treatment during a

relapse) should be treated with maintenance IP as well. Maintenance IP should be applied 3 or 4 days apart. The choice of the application days will be left to subjects' preference, and these days will be fixed throughout the trial (e.g., Thursday and Sunday); this needs to be settled at Visit 2. Subjects will be assessed by the investigator at the trial site every 4 weeks from Visit 2 to Visit 15. Furthermore, depending on when relapse occurs in relation to the regular 4-week visits (also referred to as 'scheduled' visits), additional (unscheduled) visits may be needed (outlined below).

All regular 4-week (scheduled) visits between or after an unscheduled visit or relapse follow-up visit should be performed.

Based on these rules, there are the following options:

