5.3 Baseline Considerations

5.3.1 Baseline definition

As described in the protocol, baseline is defined as the measurement taken at screening or visit 1.

The maintenance phase baseline is defined as the last available measurement collected at randomisation (visit 2).

Baseline for rebounds will be handled differently as described in section [5.5.4](#).

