SD: Standard deviation, Q1: 1st quartile, Q3: 3rd quartile, AUC: Area under the curve. AUC is calculated based on all the daily total PSI scores using the trapezoidal rule to approximate the area under and is normalised by the total number of days in the open-label phase.

Shell 45: <Change / Percent change> in total PSI score from start to end of open-label phase: open-label safety analysis set

Total PSI score from visit 1 to visit 2	Open-label safety analysis set (n=xxx)	Randomised subjects (n=xxx)	Not randomised subjects (n=xxx)
Number of subjects	xxx	xxx	xxx
Mean (SD)	xx.x (xx.x)	xx.x (xx.x)	xx.x (xx.x)
Median	xx.x	xx.x	xx.x
Q1;Q3	xx.x;xx.x	xx.x;xx.x	xx.x;xx.x
Min;Max	xx.x;xx.x	xx.x;xx.x	xx.x;xx.x

SD: Standard deviation, Q1: 1st quartile, Q3: 3rd quartile

Shell 46: Total PSI score for time on rescue medication and time in remission during the first 28 weeks of the maintenance phase: full analysis set

	LEO 90100 (n=xxx)	Vehicle (n=xxx)
Total PSI score (AUC)		
Time in remission		
Number of subjects	xxx	xxx
Mean (SD)	xx.x (xx.x)	xx.x (xx.x)
Median	xx.x	xx.x
Q1;Q3	xx.x;xx.x	xx.x;xx.x
Min;Max	xx.x;xx.x	xx.x;xx.x
Time in relapse		
Number of subjects	xxx	xxx
Mean (SD)	xx.x (xx.x)	xx.x (xx.x)
Median	xx.x	xx.x
Q1;Q3	xx.x;xx.x	xx.x;xx.x
Min;Max	xx.x;xx.x	xx.x;xx.x
Time in maintenance phase		
Number of subjects	xxx	xxx
Mean (SD)	xx.x (xx.x)	xx.x (xx.x)
Median	xx.x	xx.x
Q1;Q3	xx.x;xx.x	xx.x;xx.x
Min;Max	xx.x;xx.x	xx.x;xx.x

SD: Standard deviation, Q1:1st quartile, Q3: 3rd quartile, AUC: Area under the curve.

Average PSI score is calculated as area under the curve (AUC) over the time intervals on rescue medication

and the time intervals in remission for each subject. AUC is calculated based on all the weekly total PSI scores using the trapezoidal rule to approximate the area under and is normalised by the total number of days remission or relapse, respectively.

Shell 47: Statistical analysis of PSI: full analysis set

Weeks from randomisation	LEO 90100 vs. vehicle
Number of subjects randomised to LEO 90100	xxx
Number of subjects randomised to vehicle	xxx
Randomisation	
Estimated means	
LEO 90100	xx.xx
Vehicle	xx.xx
Treatment difference	xx.xx
95% CI	xx.xx-xx.xx
p-value	0.xxx or <0.001
Week 4	
Estimated means	
LEO 90100	
Vehicle	
Treatment difference	
95% CI	
p-value	
...	

continued...

Trial ID: LP0053-1004	Date: 15-JUL-2019	Version: 1.0
		Page 114 of 177

Weeks from randomisation	LEO 90100 vs. vehicle
Week 28	
Estimated means	
LEO 90100	
Vehicle	

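### The DLQI model takes the Visit 2 score as covariate while Shell 48 also makes it a response, so the specified REML fit has no maximum; PSI shares the defect if its two randomisation scores are one record

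*SAP*

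**What the plan says.** - **DLQI model (SAP 5.4.4.1).** The fixed terms are "treatment group, visit (scheduled), interaction between treatment and visit, relapse status", and then "maintenance baseline total DLQI score as fixed factors and subject as random effect". The covariance is unstructured and estimation is by REML. There is no baseline-by-visit term, so one slope serves all visits. Results are pooled over 100 imputed data sets and reported by visit.
- **PSI model (SAP 5.4.4.4).** The structure is the same with week in place of visit, ending with "maintenance baseline total PSI score as fixed factors and subject as random effect".
- **Baseline (SAP 5.3.1).** "The maintenance phase baseline is defined as the last available measurement collected at randomisation (visit 2").
- **Scheduled visits (Protocol 6.1.4).** Subjects are assessed "every 4 weeks from Visit 2 to Visit 15", so Visit 2 is a scheduled visit. Protocol Table 4 has DLQI collected there.
- **DLQI output (SAP Appendix II).** "Shell 48: Statistical analysis of DLQI: full analysis set" opens with a Visit 2 block of estimated means, treatment difference, 95% CI and p-value, and runs to Visit 15. Its footnote also lists "DLQI total score at time of randomisation" as a model term.
- **PSI output (SAP Appendix II).** "Shell 47: Statistical analysis of PSI: full analysis set" opens with a Randomisation block of the same form and then runs from Week 4 to Week 28. Its footnote also lists the randomisation score as a model term.

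Neither model description says at which visits or weeks the response starts.

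**The concern.** A repeated-measures model may condition on the baseline score or treat it as one of the outcomes. If it does both, with a common slope and a free variance at the baseline occasion, the fit can reproduce the baseline rows perfectly and gain unlimited likelihood by doing so.

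DLQI and PSI are the only patient-reported outcomes for which the SAP plans treatment tests, and these models replace the t-tests in Protocol 11.3.5.1 and 11.3.5.4. The SAP gives no fallback if the fit fails. The obvious rescues (removing Visit 2 from the response, removing the covariate, simplifying the covariance) are different models, and the choice should be settled before unblinding. A test at Visit 2 would in any case compare scores taken before any randomised treatment.

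**Working it through.** The plan states no figure for these models, so there is none to reproduce. The check is whether an estimate exists, and then what follows if software stops anyway.

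**1. Inputs from the documents.** Common slope, free treatment-by-visit means, unstructured covariance and REML (SAP 5.4.4.1); baseline equal to the Visit 2 score (SAP 5.3.1); a Visit 2 result required (Shell 48); 14 scheduled visits, 2 to 15. SAP Table 8 gives 132 + 55 + 52 + 68 + 56 + 68 + 114 = 545 randomised, used only to size a simulation.

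**2. Algebra.** Write B for the baseline, so the Visit 2 response is Y2 = B. For a fixed common slope b, the vector Y − bB is a linear map of (Y2, …, Y15) with determinant 1 − b. With free arm-by-visit means and an unstructured covariance:
- profile ML log-likelihood = constant − N·ln|1 − b|, which goes to infinity as b → 1;
- profile REML at fixed b has the same form with N − 2 in place of N, for the two arm means.

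Equivalently, at b = 1 every Visit 2 residual is zero. Let ε be the Visit 2 variance. As ε → 0, REML grows as −((N − 3)/2)·ln ε, because the Visit 2 rows fix two arm means and the slope. Relapse status does not interfere: the full analysis set requires treatment success at randomisation, so nobody is in relapse at Visit 2.

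**3. Numerical check.** One simulated complete data set was used: 545 subjects, 14 visits, integer scores 0 to 30, time-varying relapse. Its means, SDs and correlations are assumptions.

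| Fixed slope b | Profile REML log-likelihood |
|---|---|
| 0 | −9420.2 |
| 0.5 | −9043.8 |
| 0.9 | −8169.8 |
| 0.99 | −6919.5 |
| 0.999 | −5669.2 |
| 0.9999 | −4418.9 |

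- From b = 0.9 to 0.99 the gain is 8169.8 − 6919.5 = 1250.3. The formula gives 543 × ln 10 = 1250.3.
- Each 100-fold cut in ε adds 1248.0. The formula gives (545 − 3)/2 × ln 100 = 271 × 4.605 = 1248.0.
- Iterating REML drove the Visit 2 variance from 3.16 to 7.8 × 10⁻¹⁰ and the slope from 0.343 to 0.99999, without converging.
- The Visit 2 treatment difference and its standard error both tend to 0, so the test statistic is 0/0.
- With compound symmetry the maximum is finite (slope 0.316), so the failure needs the unstructured covariance, which is what the SAP specifies.

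**4. Same data, Visit 2 as covariate only.** REML has a finite maximum at slope 0.326.

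| | Response from Visit 3 | Limit at slope 1 | SE ratio |
|---|---|---|---|
| Visit 3 difference (SE) | −0.446 (0.189) | −0.466 (0.216) | 0.216/0.189 = 1.14 |
| Visit 15 difference (SE) | −0.366 (0.221) | −0.386 (0.289) | 0.289/0.221 = 1.31 |

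**5. Precision at slope 1 in general.** Let ρ be the correlation between Visit 2 and a later visit, and k the later SD divided by the Visit 2 SD. Per-subject variance is proportional to k² + 1 − 2ρk at slope 1, and to k²(1 − ρ²) at the best slope. The SE ratio is the square root of their quotient; for k = 1 it is √(2/(1 + ρ)).

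| | ρ = 0.7 | ρ = 0.5 | ρ = 0.3 |
|---|---|---|---|
| k = 1 | √(2/1.7) = 1.085 | √(2/1.5) = 1.155 | √(2/1.3) = 1.240 |
| k = 1.5 | √(1.15/1.1475) = 1.001 | √(1.75/1.6875) = 1.018 | √(2.35/2.0475) = 1.071 |
| k = 2 | √(2.2/2.04) = 1.038 | √(3/3) = 1.000 | √(3.8/3.64) = 1.022 |

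Equal variances therefore give 8% to 24%. For k of 1.5 to 2 the closed form gives 0% to 7%; simulation gave 0% to 8%, and I carry the wider range.

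**6. PSI.** The argument needs the covariate and the first response to be the same number. Protocol 8.13.4 uses a 24-hour recall version daily in the open-label phase and a 7-day version weekly in maintenance. The SAP does not say which record is the maintenance baseline and which fills the Randomisation block. If they are one record, steps 2 and 3 apply; if not, the residuals at slope 1 are not zero and the likelihood need not diverge.

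**The case against.** The strongest reply is that the double use comes from the shells and is not stated in the model text. SAP 5.3.1 calls Visit 2 a baseline. SAP 5.4.3 uses Visit 2 values to summarise open-label change. SAP 5.4.4 analyses outcomes collected in the maintenance phase, which Table 1 starts at first exposure to maintenance product. The shells are also loose: the footnotes to Shells 47 and 48 give days from randomisation as the time term, where the text has week and visit. A programmer could simply leave Visit 2 out of the response.

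This stands as a reading of the text, but it does not rescue the plan, because the first block of Shell 48 could then not be filled. Shell 32, the general maintenance-phase template for visits not related to relapse, also starts at Visit 2.

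Three further points stand. The PSI case is conditional. At slope 1 the harm is to precision and not to validity: in the simulated data the estimates moved by only 0.02. And an experienced programmer would probably notice a failed fit and remove Visit 2.

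A reader might infer that the fit will fail in every one of the 100 imputed data sets, or that no later-visit result can be produced. The documents do not support either. The Visit 2 identity is indeed the same in every imputed copy, but what software then does is a prediction; it may stop near slope 1 and print numbers. Nor does the subject random effect cause the failure. It cannot be separated from an unstructured covariance, but its variance can be zero, so it neither creates nor prevents the divergence.

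**Conclusion.** For DLQI the specification is wrong as written. Model text, baseline definition and Shell 48 taken together define a REML fit with no maximum and a Visit 2 test with no value. That conclusion is algebraic and does not depend on the simulated means, SDs or correlations. For PSI it holds only if the randomisation response and the maintenance baseline are one record.

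The practical size is less certain. The precision ranges in step 5 rest on assumed correlations and SD ratios, since the documents give neither. Subjects enter maintenance clear or almost clear and can relapse later, so a larger SD at later visits, and hence the smaller loss, is plausible. The 14% and 31% in step 4 belong to one simulated data set and are not estimates for this trial.

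It would be tempting to treat this as a threat to the trial's conclusions. It is not: the testing hierarchy in SAP 5.6.4 covers time to first relapse, proportion of days in remission and number of relapses, and neither DLQI nor PSI is in it. Severity is moderate.

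**What to change.** 1. In SAP 5.4.4.1, state that the response runs from Visit 3 to Visit 15, with the Visit 2 score as covariate only.
2. In SAP 5.4.4.4, state that the response starts at the first post-randomisation weekly score, and name the record (24-hour or 7-day version) that serves as maintenance baseline.
3. Delete the Visit 2 block from Shell 48 and the Randomisation block from Shell 47.
4. Drop the subject random effect from both models; the unstructured covariance already contains it.

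A covariate-by-visit interaction is optional: step 4 of the working reaches a finite maximum without one.

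The cost is SAP wording, two shells and the model statement, with no new data. It should be done before unblinding.
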